APPENDIX A: SCHEDULE OF STUDY PROCEDURES AND EVALUATIONS

Study Schedule, Group 1: Vaccination Period

Study Visit Number	V00	V01	V02	V03	V04 ^w	V05	V06
Study Day post Dose 1	Screening (Optional) D -28 to -1	Enrollment Dose 1 D1	D4[±1]	D8[+2]	D22[+7]	D25	D29
Study Day post Dose 2					Dose 2 D1	D4[±1]	D8[+2]
Obtain Informed Consent ^o	X	X [¬]					
Collect Demographic Information	X	X ^{†*}					
Review Eligibility Criteria	X	X ^{†→1}			X [†]		
Medical History [@]	X	X ^{†→*}		X	X		X
Concomitant Medications	X [‡]	X ^{†→‡}	X [‡]	X [‡]	X [‡]	X [‡]	X [‡]
Vital Signs\$ (Oral Temperature%, Pulse, and BP)	X	X [†]			X ^{†2}		
Height and Weight	X	X ^{†*}					
Physical Examination ³	X	{X} ^{†*}		{X}	{X}		{X}
Urine or Serum Pregnancy Test	X [^]	X ^{†^}			X ^{†^}		
Venous Blood Collection for ESR	X	X ^{‡*}					
Venous Blood Collection for Clinical Safety Laboratory Evaluations~		X [†]		X	X [†]		X
Venous Blood Collection for Immunogenicity Assays		X [†]			X [†]		
Serum Sample Collected for Future Research ⁴		X [†]		X	X [†]		X
Safety Follow-up Phone Call			X			X	

Study Visit Number	V00	V01	V02	V03	V04 [¶]	V05	V06
Study Day post Dose 1	Screening (Optional) D-28 to -1	Enrollment Dose 1 D1	D4[±1]	D8[+2]	D22[+7]	D25	D29
Study Day post Dose 2						D4[±1]	D8[+2]
Enrollment in AdvantageEDC SM and Randomization		X [†]					
Pre-Administration Reactogenicity Assessments		X [†]			X		
Vaccination		X			X		
20-minute Evaluation After Study Vaccination		X			X		
Examine Study Vaccination Site		X		X	X		X
Post-Administration Reactogenicity Assessments		X			X		
Distribute Memory Aid and Study-Related Materials		X			X		
Review Memory Aid			X	X		X	X
AE/SAE Assessment		X ^{&}	X ^{&}	X ^{&}	X ^{&}	X ^{&}	X ^{&}

[∞] Prior to study procedures.

[†] Prior to study vaccination.

¹ Review results of clinical screening (ESR) or safety laboratory evaluations.

[–] Review/confirm information or activity in subjects previously consented and screened.

^② Complete medical history will be obtained by interview of subjects at screening (optional) or on Day 1 prior to the first study vaccination and interim medical history will be obtained by interview of subjects at follow-up visits after Dose 1

^④ Receipt of non-study influenza vaccines will be solicited through approximately 180 days after the last study vaccination, and reported in the eCRF.

^{*} Not required if done at the optional screening visit.

[√] All current medications and medications taken within 60 days prior to signing the ICF.

[§] Vital signs assessed on Day 1 prior to the first study vaccination will be considered as baseline.

[%] Subjects must not eat or drink anything hot or cold, or smoke within 10 minutes prior to taking oral temperature.

² Vital signs are not required for subjects who are discontinued from receipt of the third study vaccination and are being followed for safety.

³ At the screening (or baseline if not done at screening) visit, a physical examination will be performed on all subjects to include the following organs and organ systems: skin, head and neck, lungs, heart, liver, spleen, extremities, lymph nodes, and nervous system.

^{} Targeted physical examination if indicated based on review of interim medical history.

[^] May be performed on all women of childbearing potential at screening (optional) and will be performed within 24 hours prior to each vaccination and results must be negative and known prior to each study vaccination.

[‡] To be performed locally by the site. The ESR value must be confirmed as <30 mm/hr prior to randomization and first study vaccination.

[~] Includes WBC, Hgb, PLT, ALT, T. Bili, Cr.

[¶] Subjects who do not receive the third study vaccination will continue with follow-up safety assessments (may be conducted by phone call) rather than in person continuing through approximately 12 months after their first study vaccination. These subjects will also be encouraged to provide a venous blood sample for immunogenicity assays at approximately 21 and 180 days after their first study vaccination.

[§] For subjects who have consented to collect serum for future research.

[&] Inclusive of reactogenicity assessments performed on the day of each vaccination through 7 days after each study vaccination.

Study Schedule, Group 1: Follow-up Period

Study Visit Number	V07	V08	V09 [¶]	V10	V11	Early Termination (if needed)	Unscheduled (if needed)
Study Day post Dose 1	D43	D64	D181 [±14]	D202	D387		
Study Day post Dose 2	D22[+7]	D43[+7]		D181[±14]	D366[±14]		
Medical History [§]	X	X	X	X		X	X (if indicated)
Concomitant Medications	X [¶]	X [¶]	X [¶]	X [¶]		X (if within 21 days after last study vaccination and receipt of any non-study influenza vaccine will be recorded if within 180 days after the 2nd study vaccination)	X (if within 21 days after last study vaccination and receipt of any non-study influenza vaccine will be recorded if within 180 days after the 2nd study vaccination)
Vital Signs\$ (Oral Temperature%, Pulse, and BP)						X (may be obtained if indicated)	X (may be obtained if indicated)
Physical Examination ^³	{X}	{X}	{X}	{X}		{X}	{X}
Venous Blood Collection for Clinical Safety Laboratory Evaluations [~]						X (if within 7 days after the last study vaccination)	X (if indicated)
Venous Blood Collection for Immunogenicity Assays	X		X	X		X(if within 21 days after last study vaccination)	X(if within 21 days after last study vaccination)
Serum Sample Collected for Future Research ^⁴	X	X	X	X		X(if within 21 days after last study vaccination)	X(if within 21 days after last study vaccination)

Safety Follow-up Phone Call					X		
Examine Study Vaccination Site						X (if within 7 days after last study vaccination)	X (if within 7 days after last study vaccination)
Post-Administration Reactogenicity Assessments						X (if within 7 days after last study vaccination)	X (if within 7 days after last study vaccination)
Review Memory Aid						X (if within 7 days after last study vaccination)	X (if within 7 days after last study vaccination)
AE/SAE Assessment	X	X	X	X	X	X&	X&

^a Complete medical history will be obtained by interview of subjects at screening (optional) or on Day 1 prior to the first study vaccination and interim medical history will be obtained by interview of subjects at follow-up visits after Dose 1

^c Receipt of non-study influenza vaccines will be solicited through approximately 180 days after the last study vaccination, and reported in the eCRF.

^s Vital signs assessed on Day 1 prior to the first study vaccination will be considered as baseline.

[%] Subjects must not eat or drink anything hot or cold, or smoke within 10 minutes prior to taking oral temperature.

^{} Targeted physical examination if indicated based on review of interim medical history

[~] Includes WBC, Hgb, PLT, ALT, T. Bili, Cr.

[¶] Subjects who do not receive the third study vaccination will continue with follow-up safety assessments (may be conducted by phone call) rather than in person continuing through approximately 12 months after their first study vaccination. These subjects will also be encouraged to provide a venous blood sample for immunogenicity assays at approximately 21 and 180 days after their first study vaccination.

⁴ For subjects who have consented to collection of serum for future use.

Study Schedule, Group 2: Vaccination Period

Study Visit Number	V00	V01	V02	V03	V04 [¶]	V05	V06	V07 [¶]	V08
Study Day post Dose 1	Screening (Optional) D-28 to -1	Enrollment Dose 1 D1	D4[±1]	D8[+2]	D22[+7]	D25	D29	D43	D46
Study Day post Dose 2					Dose 2 D1	D4[±1]	D8[+2]	D22[+7]	D25
Study Day post Dose 3								D4[±1]	D46
Study Procedure/Evaluation									
Obtain Informed Consent [∞]	X	X [¬]							
Collect Demographic Information	X	X ^{†*}							
Review Eligibility Criteria	X	X ^{†-1}		X [†]			X [†]		
Medical History [¶]	X	X ^{†-*}	X	X		X	X		

Study Visit Number	V00	V01	V02	V03	V04 ^w	V05	V06	V07 ^w	V08
Study Day post Dose 1	Screening (Optional) D-28 to -1	Enrollment Dose 1 D1	D4[±1]	D8[+2]	Dose 2 D1	D22[+7]	D4[±1]	D8[+2]	Dose 3 D1
Study Day post Dose 2									
Study Day post Dose 3									
Study Procedure/Evaluation									
Concomitant Medications	X ^c	X ^{†→c}	X ^c	X ^c	X ^c	X ^c	X ^c	X ^c	X ^c
Vital Signs\$ (Oral Temperature%, Pulse, and BP)	X	X [†]			X ^{†2}			X ^{†2}	
Height and Weight	X	X ^{†*}							
Physical Examination ³	X	X ^{†*}		{X}	{X}		{X}	{X}	
Urine or Serum Pregnancy Test	X [^]	X ^{†^}			X ^{†^}			X ^{†^}	
Venous Blood Collection for ESR	X	X ^{‡*}							
Venous Blood Collection for Clinical Safety Laboratory Evaluations~		X [†]		X	X [†]		X	X [†]	
Venous Blood Collection for Immunogenicity Assays		X [†]			X [†]			X [†]	
Serum Sample Collected for Future Research ⁴		X [†]		X	X [†]		X	X [†]	
Safety Follow-up Phone Call			X			X			X
Enrollment in AdvantageEDC SM and Randomization		X [†]							
Pre-Administration Reactogenicity Assessments		X [†]			X			X	
Vaccination		X			X			X	
20-minute Evaluation After Vaccination		X			X			X	
Examine Vaccination Site		X		X	X		X	X	

Study Visit Number	V00	V01	V02	V03	V04 ^w	V05	V06	V07 ^w	V08
Study Day post Dose 1	Screening (Optional) D-28 to -1	Enrollment Dose 1 D1	D4[±1]	D8[+2]	Dose 2 D1	D22[+7]	D4[±1]	D22[+7]	D46
Study Day post Dose 2							D8[+2]		D25
Study Day post Dose 3								Dose 3 D1	D43
Study Procedure/Evaluation									
Post-Administration Reactogenicity Assessments		X			X			X	
Distribute Memory Aid and Study-Related Materials		X			X			X	
Review Memory Aid			X	X		X	X		X
AE/SAE Assessment		X&	X&	X&	X&	X&	X&	X&	X&

^o Prior to study procedures.

[†] Prior to study vaccination.

¹ Review results of clinical screening (ESR) or safety laboratory evaluations.

[–] Review/confirm information or activity in subjects previously consented and screened.

[®] Complete medical history will be obtained by interview of subjects at screening (optional) or on Day 1 prior to the first study vaccination and interim medical history will be obtained by interview of subjects at follow-up visits after the first study vaccination.

[¤] Receipt of non-study influenza vaccines will be solicited through approximately 180 days after the last study vaccination, and reported in the eCRF.

^{*} Not required if done at the optional screening visit.

[√] All current medications and medications taken within 60 days prior to signing the ICF.

[§] Vital signs assessed on Day 1 prior to the first study vaccination will be considered as baseline.

[%] Subjects must not eat or drink anything hot or cold, or smoke within 10 minutes prior to taking oral temperature.

² Vital signs are not required for subjects who are discontinued from receipt of the third study vaccination and are being followed for safety.

³ At the screening (or baseline if not done at screening) visit, a physical examination will be performed on all subjects to include the following organs and organ systems: skin, head and neck, lungs, heart, liver, spleen, extremities, lymph nodes, and nervous system.

^{} Targeted physical examination if indicated based on review of interim medical history.

[^] May be performed on all women of childbearing potential at screening (optional) and will be performed within 24 hours prior to each vaccination and results must be negative and known prior to each study vaccination.

[#] To be performed locally by the site. The ESR value must be confirmed as <30 mm/hr prior to randomization and first study vaccination.

[~] Includes WBC, Hgb, PLT, ALT, T. Bili, Cr.

[¶] Subjects who do not receive the third study vaccination will continue with follow-up safety assessments (may be conducted by phone call) rather than in person continuing through approximately 12 months after their first study vaccination. These subjects will also be encouraged to provide a venous blood sample for immunogenicity assays at approximately 21 and 180 days after their first study vaccination.

⁴ For subjects who have consented to collect serum for future use.

[&] Inclusive of reactogenicity assessments performed on the day of each vaccination through 7 days after each study vaccination.

Study Schedule, Group 2: Follow-up Period

Study Visit Number	D8[+2]	D29	D50	V09	D64	V10	D181 [±14]	V11 ^ψ	Early Termination (if needed)	Unscheduled (if needed)
Study Day post Dose 1										
Study Day post Dose 2										
Study Day post Dose 3										
Medical History [ⓐ]	X	X	X	X					X	X (if indicated)
Concomitant Medications	X [¢]	X [¢]	X [¢]	X [¢]					X (if within 21 days after last study vaccination and receipt of any non-study influenza vaccine will be recorded if within 180 days after the 2nd study vaccination)	X (if within 21 days after last study vaccination and receipt of any non-study influenza vaccine will be recorded if within 180 days after the 2nd study vaccination)
Vital Signs ^{\$} (Oral Temperature%, Pulse, and BP)									X (may be obtained if indicated)	X (may be obtained if indicated)
Physical Examination ^³	{X}	{X}	{X}	{X}					{X}	{X}
Venous Blood Collection for Clinical Safety Laboratory Evaluations [~]	X								X (if within 7 days after the last study vaccination)	X (if indicated)
Venous Blood Collection for Immunogenicity Assays		X	X	X					X(if within 21 days after last study vaccination)	X(if within 21 days after last study vaccination)
Serum Sample Collected for Future Research ^⁴	X	X	X	X					X(if within 21 days after last study vaccination)	X(if within 21 days after last study vaccination)
Safety Follow-up Phone Call					X					
Examine Vaccination Site	X								X (if within 7 days after last study vaccination)	X (if within 7 days after last study vaccination)
Post-Administration Reactogenicity Assessments									X (if within 7 days after last study vaccination)	X (if within 7 days after last study vaccination)
Review Memory Aid	X								X (if within 7 days after last study vaccination)	X (if within 7 days after last study vaccination)
AE/SAE Assessment	X&	X	X	X	X				X&	X&

[ⓐ] Complete medical history will be obtained by interview of subjects at screening (optional) or on Day 1 prior to the first study vaccination and interim medical history will be obtained by interview of subjects at follow-up visits after the first study vaccination.

[¢] Receipt of non-study influenza vaccines will be solicited through approximately 180 days after the last study vaccination, and reported in the eCRF.

[§] Vital signs assessed on Day 1 prior to the first study vaccination will be considered as baseline.

[%] Subjects must not eat or drink anything hot or cold, or smoke within 10 minutes prior to taking oral temperature.

^{} Targeted physical examination if indicated based on review of interim medical history.

[~] Includes WBC, Hgb, PLT, ALT, T. Bili, Cr.

[¶] Subjects who do not receive the second or third study vaccination will continue with follow-up safety assessments (may be conducted by phone call) rather than in person continuing through approximately 12 months after their first study vaccination. These subjects will also be encouraged to provide a venous blood sample for immunogenicity assays at approximately 21 and 180 days after their first study vaccination.

⁴ For subjects who have consented to collect serum for future use

[&] Inclusive of reactogenicity assessments performed on the day of each study vaccination through 7 days after each study vaccination.

Study Schedule, Group 3: Vaccination and Follow-up Periods

Study Visit Number	V00	V01	V02	V03	V04 [¶]	V05	V06	V07 [¶]	V08
Study Day post dose	Screening (Optional) D-28 to -1	Enrollment Dose 1 D1	D4[±1]	D8[+2]	D22[+7]	D43[+7]	D64[+7]	D181[±14]	D366[±14]
Obtain Informed Consent	X	X [¬]							
Collect Demographic Information	X	X ^{†*}							
Review Eligibility Criteria	X	X ^{†→1}							
Medical History [@]	X	X ^{†→*}		X	X	X	X	X	
Concomitant Medications	X [§]	X ^{†→§}	X [§]	X [§]	X [§]	X [§]	X [§]	X [§]	
Vital Signs\$ (Oral Temperature [‰] , Pulse, and BP)	X	X [†]							
Height and Weight	X	X ^{†*}							
Physical Examination ³	X	{X} ^{†*}		{X}	{X}	{X}	{X}	{X}	
Urine or Serum Pregnancy Test	X [^]	X ^{†^}							
Venous Blood Collection for ESR	X	X ^{‡*}							
Venous Blood Collection for Clinical Safety Laboratory Evaluations~		X		X					
Venous Blood Collection for Immunogenicity Assays		X [†]			X			X	
Serum Sample Collected for Future Research ⁴		X [†]		X	X	X	X	X	
Safety Follow-up Phone Call			X						X
Enrollment in AdvantageEDC SM and Randomization		X [†]							
Pre-Administration Reactogenicity Assessments		X [†]							
Vaccination		X							

Study Visit Number	V00	V01	V02	V03	V04 ^w	V05	V06	V07 ^w	V08
Study Day post dose	Screening (Optional) D-28 to -1	Enrollment Dose 1 D1	D4[±1]	D8[+2]	D22[+7]	D43[+7]	D64[+7]	D181[±14]	D366[±14]
20-minute Evaluation After Vaccination		X							
Examine Vaccination Site		X		X					
Post-Administration Reactogenicity Assessments		X							
Distribute Memory Aid and Study-Related Materials		X							
Review Memory Aid			X	X					
AE/SAE Assessment	X ^{&}	X ^{&}	X ^{&}	X ^{&}	X	X	X	X	X

[∞] Prior to study procedures.

[†] Prior to study vaccination.

¹ Review results of clinical screening (ESR) or safety laboratory evaluations.

[–] Review/confirm information or activity in subjects previously consented and screened

[@] Complete medical history will be obtained by interview of subjects at screening (optional) or on Day 1 prior to study vaccination and interim medical history will be obtained by interview of subjects at follow-up visits after the study vaccination.

[¤] Receipt of non-study influenza vaccines will be solicited through approximately 180 days after the study vaccination, and reported in the eCRF.

^{*} Not required if done at the optional screening visit.

[√] All current medications and medications taken within 60 days prior to signing the ICF.

[§] Vital signs assessed on Day 1 prior to the study vaccination will be considered as baseline.

[%] Subjects must not eat or drink anything hot or cold, or smoke within 10 minutes prior to taking oral temperature.

^³ At the screening (or baseline if not done at screening) visit, a physical examination will be performed on all subjects to include the following organs and organ systems: skin, head and neck, lungs, heart, liver, spleen, extremities, lymph nodes, and nervous system.

^{} Targeted physical examination if indicated based on review of interim medical history.

[^] May be performed on all women of childbearing potential at screening (optional) and will be performed within 24 hours prior to study vaccination and results must be negative.

[#] To be performed locally by the site. The ESR value must be confirmed as <30 mm/hr prior to randomization and study vaccination.

[~] Includes WBC, Hgb, PLT, ALT, T. Bili, Cr.

^⁴ For subjects who have consented to collection of serum for future use.

[&] Inclusive of reactogenicity assessments performed on the day of vaccination through 7 days after study vaccination.

Early Termination and Unscheduled Visits, Group 3

Study Visit Number	Early Termination (if needed)	Unscheduled (if needed)
Study Day post dose		
Medical History [@]	X	X (if indicated)

Concomitant Medications	X (if within 21 days after last study vaccination and receipt of any non-study influenza vaccine will be recorded if within 180 days after the 2nd study vaccination)	X (if within 21 days after last study vaccination and receipt of any non-study influenza vaccine will be recorded if within 180 days after the 2nd study)
Vital Signs (Oral Temperature ^{%,} , Pulse, and BP)	X (may be obtained if indicated)	X (may be obtained if indicated)
Physical Examination ³	{X}	{X}
Venous Blood Collection for Clinical Safety Laboratory Evaluations [~]	X (if within 7 days after the last study vaccination)	X (if indicated)
Venous Blood Collection for Immunogenicity Assays	X (if within 21 days after last study vaccination)	X (if within 21 days after last study vaccination)
Serum Sample Collected for Future Research ⁴	X(if within 21 days after last study vaccination	X(if within 21 days after last study vaccination
Examine Vaccination Site	X (if within 7 days after last study vaccination)	X (if within 7 days after last study vaccination)
Post-Administration Reactogenicity Assessments	X (if within 7 days after last study vaccination)	X (if within 7 days after last study vaccination)
Review Memory Aid	X (if within 7 days after last study vaccination)	X (if within 7 days after last study vaccination)
AE/SAE Assessment	X&	X&

³ Complete medical history will be obtained by interview of subjects at screening (optional) or on Day 1 prior to study vaccination and interim medical history will be obtained by interview of subjects at follow-up visits after the study vaccination.

⁴ Vital signs assessed on Day 1 prior to the study vaccination will be considered as baseline.

[~] Subjects must not eat or drink anything hot or cold, or smoke within 10 minutes prior to taking oral temperature.

⁴ Targeted physical examination if indicated based on review of interim medical history.

[~] Includes WBC, Hgb, PLT, ALT, T. Bili, Cr.

⁴ For subjects who have consented to collection of serum for future use.

[&] Inclusive of reactogenicity assessments performed on the day of vaccination through 7 days after study vaccination.

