3.2 Study Outcome Measures

3.2.1 Primary

Safety:

- Occurrence of all SAEs following the first study vaccination through approximately 12 months after the last study vaccination.
- Occurrence of study vaccine-related SAEs following the first study vaccination through approximately 12 months after the last study vaccination.
- Occurrence of solicited injection site and systemic AEs following each study vaccination through 7 days after each study vaccination.
- Occurrence of clinical safety laboratory AEs following each study vaccination through approximately 7 days after each study vaccination.

Immunogenicity:

- For HAI and Neut antibodies, percentage of subjects achieving seroconversion against the 2017 H7N9 study vaccine strain (defined as either a pre-vaccination titer $<1:10$ and a post-vaccination titer $\geq 1:40$ or a pre-vaccination titer $\geq 1:10$ and a minimum four-fold rise in post-vaccination antibody titer) at approximately 21 days after 2 doses of AS03-adjuvanted 2017 H7N9 IIV (Group 1 – Day 43; Group 2 – Day 64; Group 3 – N/A).
- For HAI and Neut antibodies, percentage of subjects achieving seroconversion against each of the study IIV4 strains at approximately 21 days after receipt of study IIV4 (Groups 1, 2 and 3 – Day 22).
- For HAI and Neut antibodies, percentage of subjects with an antibody titer of $\geq 1:40$ against the influenza 2017 H7N9 study vaccine strain at approximately 21 days following

receipt of 2 doses of AS03-adjuvanted 2017 H7N9 IIV (Group 1 – Day 43; Groups 2 – Day 64; Group 3 – N/A).

- For HAI and Neut antibodies, percentage of subjects with an antibody titer of $\geq 1:40$ against each of the study IIV4 strains at approximately 21 days after receipt of study IIV4 (Groups 1, 2 and 3 – Day 22).
- GMTs of serum HAI and Neut antibodies against the 2017 H7N9 IIV strain at approximately 21 days following receipt of 2 doses of AS03-adjuvanted 2017 H7N9 IIV (Group 1 – Day 43; Group 2 – Day 64; Group 3 – N/A).
- GMTs of serum HAI and Neut antibodies against each of the 2017 IIV4 strains at approximately 21 days after receipt of IIV4 (Group 1, 2 and 3 – Day 22).

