5.2.4 Handling of Withdrawals and Discontinuation of Treatment

The primary reason for withdrawal from this trial will be recorded on the Study Status data collection form (DCF). Subjects will be encouraged to complete the Early Termination Visit. The Early Termination Visit procedures are listed in [Section 8.5](#).

Although subjects are free to withdraw at any time or may be withdrawn by the site principal investigator or appropriate sub-investigator at any time (see [Section 5.2.3](#)), those subjects do not receive Dose 2 or Dose 3 of study vaccine will be encouraged to remain in this trial for follow-up safety assessments (may be conducted by phone call rather than in person) continuing through approximately 12 months after their last study vaccination. These subjects will also be encouraged to provide a venous blood sample for immunogenicity assays at approximately 21 days and 180 days after their last study vaccination, if applicable. See the protocol-specific Manual of Procedures (MOP) for alternate follow-up requirements.

Every attempt will be made to follow all AEs, including solicited injection site and systemic reactions, unsolicited non-serious AEs, SAEs and MAAEs, including NOCMCs and PIMMCs, ongoing at the time of early withdrawal through resolution as per applicable collection times defined for the specific type of AE.

In the case of subjects who fail to appear for a follow-up safety assessment, extensive effort (i.e., three documented contact attempts via phone calls made on separate occasions and followed by a certified letter) will be made to locate or recall them, or at least to determine their health status. These efforts will be documented in the subject's study records.

Subjects who withdraw, or are withdrawn or terminated from this trial, or are lost to follow-up after signing the informed consent form (ICF), randomization, and receipt of study vaccine will not be replaced. However, if a subject withdraws after signing the ICF, but before randomization and/or receipt of study vaccine, they may be replaced.

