8 STUDY SCHEDULE

Complete study schedule details listed by type of visit are described below. Refer also to [Sections 4](#) and [7](#) and [Appendix A: Schedule of Study Procedures and Evaluations](#). For detailed information regarding the study schedule for discontinued subjects, please reference the MOP—Discontinued Subjects Remaining on Study.

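### Group 2 subjects who receive Dose 2 but not Dose 3: the schedule footnotes end safety follow-up 12 months after the first vaccination, while section 5.2.4 and the SAE and MAAE endpoints count from the last

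*Protocol*

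**What the plan says.** **Schedule footnotes.** In Appendix A, the footnote to the Group 2 vaccination-period table covers subjects who miss the third study vaccination. The one to the follow-up-period table is wider: "Subjects who do not receive the second or third study vaccination will continue with follow-up safety assessments". Both run safety follow-up "continuing through approximately 12 months after their first study vaccination" and encourage blood for "immunogenicity assays at approximately 21 and 180 days after their first study vaccination". SAP Tables 4 and 5 reproduce both footnotes with the same anchors.

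**Body of the protocol.** Section 5.2.4 addresses the same people, those who do not receive Dose 2 or Dose 3. It takes safety follow-up "continuing through approximately 12 months after their last study vaccination" and encourages blood "at approximately 21 days and 180 days after their last study vaccination, if applicable".

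**Endpoints and reporting.** The first primary safety outcome in section 3.2.1 is "Occurrence of all SAEs following the first study vaccination through approximately 12 months after the last study vaccination". Section 3.2.2 gives MAAEs, NOCMCs and PIMMCs the same window, and SAP 3.2.1 and 3.2.2 match. Sections 6.6, 9.1, 9.3 and 9.4 also place the end of the reporting period about 12 months after the last vaccination.

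**Pointer to another document.** Section 5.2.4 refers to the MOP "for alternate follow-up requirements", and section 8 does so for "detailed information regarding the study schedule for discontinued subjects".

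**The concern.** The footnotes sit in the visit tables and state an end to follow-up that disagrees with the rest of the plan. For one kind of subject the difference is real: someone in Group 2 given IIV4 on Day 1 and one dose of H7N9/AS03 three to four weeks later, and no Dose 3. If a site works from the footnote, the last safety contact comes before 12 months have passed since that subject's only dose of the investigational vaccine. New SAEs and MAAEs that begin in the final weeks of the endpoint window could then go unrecorded.

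These subjects are not a neutral subset. Under section 5.2.3, Dose 3 can be withheld because of a Grade 3 event without another cause after a vaccination, or because of a hospitalization.

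The same footnotes also time the encouraged samples from Day 1, so they leave out a sample that section 5.2.4 asks for.

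**Working it through.** **Who is affected.**
- Group 1 subject who misses the third vaccination: both earlier injections were given on Day 1, so first and last coincide. No conflict.
- Group 2 subject who stops after IIV4: the only vaccination was on Day 1. No conflict.
- Group 2 subject with Dose 2 but not Dose 3: first is Day 1; last is Day 22 to Day 29 (section 8.3.3, 21 (+7) days after Day 1). Conflict.

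**Day convention.** Study day = dose day + offset. This reproduces the plan's own calendar at offsets of 21, 180 and 365 days:
- a Day 1 dose gives 22, 181 and 366 (Group 3);
- a Day 22 dose gives 43, 202 and 387 (Group 1, Dose 2);
- a Day 43 dose gives 64, 223 and 408 (Group 2, Dose 3).

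**Applied to the affected subject.**

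| | Footnotes (from Day 1) | 5.2.4, Dose 2 on Day 22 | 5.2.4, Dose 2 on Day 29 |
|---|---|---|---|
| 21-day sample | Day 22 | Day 43 | Day 50 |
| 180-day sample | Day 181 | Day 202 | Day 209 |
| End of safety follow-up | Day 366 | Day 387 | Day 394 |

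Follow-up after Dose 2 under the footnote:
- Dose 2 on Day 22: 366 − 22 = 344 days; shortfall 387 − 366 = 21 days; 21/365 = 5.8%.
- Dose 2 on Day 29: 366 − 29 = 337 days; shortfall 394 − 366 = 28 days; 28/365 = 7.7%.

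**Does a visit tolerance close the gap?** The documents give none for discontinued subjects. Assume the ±14 days of the routine final call (section 8.3.12) for both anchors. A footnote-timed call then falls on Days 352 to 380.
- Dose 2 on Day 22: the required window is Days 373 to 401. The overlap is Days 373 to 380, or 8 of 29 days.
- Dose 2 on Day 29: the required window is Days 380 to 408. The overlap is Day 380 only, or 1 of 29 days.

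A call on the nominal Day 366 lies outside both required windows.

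**Samples, checked against the visit schedule.** Visit 07 (section 8.3.6) is set 21 (+7) days after Dose 2, includes an antibody draw, and has a note for subjects discontinued from Dose 3. The 21-day draw after Dose 2 is therefore already scheduled. For 180 days after Dose 2, Visit 11 on Day 181 comes 181 − 22 = 159 or 181 − 29 = 152 days after that dose, and Visit 12 is timed from Dose 3. No visit is set for about Day 202 to 209.

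**Number of subjects.** Not stated. Section 11.4.2 allows for up to 15% excluded from the per-protocol analysis after dose 3, for missed doses, loss to follow-up and deviations together: 0.15 × 60 = 9 in Group 2. Those with Dose 2, without Dose 3 and still in follow-up are only part of that.

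**The case against.** The best defence is that every operative section agrees. Section 5.2.4, the endpoint definitions, and sections 6.6, 9.1, 9.3 and 9.4 all use the last vaccination; only a table footnote, and its SAP copy, which does not direct sites, differ. Both rules are stated as approximate, and the MOP is named as the place for discontinued-subject scheduling. SAEs and MAAEs are reported as listings (section 11.6.2), so no estimate or test changes. This defence holds for the size of the effect. It does not remove the contradiction, and the tolerance check shows that an approximate date reconciles the two anchors only for a late call.

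Three stronger readings are tempting, and the documents do not support them.

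- *Follow-up will in fact be cut short for these subjects.* That depends on what sites do, and the MOP is not among the documents.
- *Known events are dropped.* Section 9.4 has SAEs and MAAEs, including NOCMCs and PIMMCs, followed to resolution even past the reporting period. Section 9.3.1 keeps related SAEs reportable after the trial if the investigator learns of them. What remains exposed is an event whose onset falls after an early last contact, other than a related SAE that later comes to light.
- *No post-H7N9 sample is planned, because the footnote's 21-day sample falls on or before the day of Dose 2.* Visit 07 already provides that draw.

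The Day 1 anchor is also partly right for samples: Day 181 is the 180-day draw for the IIV4 strains. Replacing *first* by *last* throughout would remove it.

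**Conclusion.** The footnotes are wrong as written for one narrow class: Group 2 subjects with Dose 2 and no Dose 3. For them the footnotes end nominal safety follow-up at Day 366 instead of Day 387 to 394, so the primary SAE window and the secondary MAAE, NOCMC and PIMMC window fall 21 to 28 days short after the only H7N9/AS03 dose. The footnotes also omit the encouraged sample at about Day 202 to 209.

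The effect is very small: an unstated number of subjects, within a planning ceiling of 9 for all causes of exclusion. Group 1, membership of the mITT population and the primary two-dose H7N9 endpoint are untouched. Those subjects could not contribute to the 180-day endpoint after two doses in any case.

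The contradiction in the text is certain. Actual loss of follow-up is conditional on a site following the footnote rather than section 5.2.4 or the MOP. The overlap figures rest on the assumed ±14 days.

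**What to change.** In the four Group 2 footnotes (two in Appendix A, and those in SAP Tables 4 and 5):

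1. Change the anchor for safety follow-up from the first to the last study vaccination.
2. For samples, keep the Day 181 draw for the IIV4 strains and add draws 21 and 180 days after the last study vaccination, if applicable. Visit 07 already meets the 21-day draw after Dose 2.
3. Check that the MOP section on discontinued subjects says the same.

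The cost is footnote wording, a final call three to four weeks later for a few subjects, and one further encouraged sample at about Day 202 to 209 for those willing to give it.
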